### 10.3. COVID-19 IMPACT

The impact of COVID-19 on study related visits are collected on 'Pandemic Visit Impact' in eCRF. Impact information will be presented in a data listing for Run-in period population.

## 11. DEMOGRAPHIC AND OTHER BASELINE CHARACTERISTICS

Demographic data and other baseline characteristics will be summarized by the planned treatment group for the Runin period population.

No statistical testing will be carried out for demographic or other baseline characteristics.

The following demographic and other baseline characteristics will be reported for this study:

Age (years) - calculated relative to date of consent

Document: \\ieedc-vnasc01\Biosdata\\Viatris\HULIO\HAB34991\Biostatistics\Documentation\SAP

Author: Version Number: 2.0

Version Date: 29Nov2023

Template No.: CS\_TP\_BS016 Revision 7 Reference: CS\_WI\_BS005

Effective Date: 01Nov2021

Page 25 of 48

- Sex
- Childbearing potential
- Race
- Ethnicity
- Baseline Weight (kg)
- Baseline Height (cm)
- Baseline PASI score
- Baseline sPGA Total Average score and Severity Score (0-5 scale)
- BMI (kg/m²)
- A listing of patient demographic data and other baseline characteristics will be presented for the Run-in period population.

#### 11.1. Derivations

• BMI  $(kg/m^2)$  = weight (kg)/ height  $(m)^2$ 

## 12. MEDICAL HISTORY AND PROCEDURES/SURGICAL HISTORY

Medical History information is obtained from the 'Medical History' form of the eCRF. Medical History will be coded using the Medical Dictionary for Regulatory Activities (MedDRA, Version 25.1 or latest) dictionary and summarized using SOC and PT for Run-in period population. A listing of medical history will be provided.

Status of heart failure and NYHA class will be summarized.

Procedures/Surgical History will be summarized separately by system organ class (SOC) and preferred term (PT) by planned treatment group for the Run-in period Population. A separate listing for Procedure/Surgical History information collected on eCRF form "Procedure/Surgical History" will be presented by planned treatment group for the Run-in period Population. Information collected on eCRF form "Subject History" will also be listed.

### 13. CONCOMITANT DISEASE

Concomitant Disease will be presented for the Run-in period population. A listing of concomitant disease will be provided. Information collected "Concomitant Disease" section in "Medical history" eCRF form will be presented.

 Concomitant Disease will be coded using Medical Dictionary for Regulatory Activities (MedDRA, Version 25.1 or latest) dictionary.

Document: \\ieedc-vnasc01\Biosdata\\Viatris\HULIO\HAB34991\Biostatistics\Documentation\SAP

Author: Version Number: 2.0

Version Date: 29Nov2023

Template No.: CS\_TP\_BS016 Revision 7 Reference: CS\_WI\_BS005

Effective Date: 01Nov2021

Page 26 of 48

- Concomitant Disease are conditions which started prior to or at Screening and are ongoing at the date of Screening or ended after screening. Any conditions which started after the first dose of study medication are also considered as Concomitant Disease.
- Presented by SOC and PT.
- Concomitant Disease information is obtained from the 'Medical History' form of the eCRF with Ongoing status as 'Yes' or have start date after the treatment start date.

#### 14. **MEDICATIONS**

Prior and Concomitant medications will be presented for the Run-in Period Population and coded using WHO Drug dictionary Version 202303 B3. Medications are recorded in the form 'Prior and Concomitant Medications' of the eCRF.

See Appendix 3 for handling of partial dates for medications, in the case where it is not possible to define a medication as prior, or concomitant, the medication will be classified by the worst case, i.e., concomitant.

Prior and concomitant medications will be summarized by primary therapeutic subgroup (3rd level ATC code) and preferred name.

- 'Prior' medications are medications which started and stopped prior to the first dose of study medication (i.e., first dose of Humira in the Run-in Period).
- 'Concomitant' medications are medications which:
  - started prior to, on or after the first dose of study medication (i.e., first dose of Humira in the Run-in Period).
  - AND ended on or after the date of first dose of study medication or were ongoing at the end of the study.

If Concomitant medication started and ended during Run-in period, it will be part of Run-in period. If concomitant medication started during Run-in period and end date is missing it will be part of Run-in period. If concomitant medication started during Randomized Interchangeable Treatment Period, it will be part of Randomized Interchangeable Treatment Period. If start and stop date of concomitant medication is missing, then it will be part of Run-in period.

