### 7. GENERAL CONSIDERATIONS

### 7.1. Reference Start Date and Study Day

All summaries by period defined in the SAP refers to the analysis period. The analysis period consists of screening, Run-in Period, and Randomized Interchangeable Treatment Period (study diagram). Each period is defined as below:

Screening period is defined as study period from informed consent date prior to administration of Humira at Week 1.

Run-in Period is defined as study period on or after administration of Humira at Week 1 and before randomization at Week 12, or until last study participation date if patients withdrew/discontinued before Week 12.

Randomized Interchangeable Treatment Period is defined as study period from the randomization at Week 12 until Week 28 or until last study participation date if patients withdrew/discontinued. While presenting the data Week 28 (EOT) assessment will also be included.

Overall period is defined as study period consisting of above 3 periods and including follow up (Week 30/EOS). Study Day will be calculated from the reference start date and will be used to show start/stop day of assessments and events. It will appear in every listing where an assessment date or event date appears.

Reference start date is defined as the day of the first dose of study medication, i.e., Humira in the Run-in Period (Week 1/Visit 1) (Day 1 is the day of the first dose of study medication).

- If the date of the event is on or after the reference date, then:
- Study Day = (date of event reference date) + 1.
- If the date of the event is prior to the reference date, then:
- Study Day = (date of event reference date).

In the situation where the event date is partial or missing, Study Day, and any corresponding durations will appear

Document: \\ieedc-vnasc01\Biosdata\Viatris\HULIO\HAB34991\Biostatistics\Documentation\SAP

Author: Version Number: 2.0

Version Date: 29Nov2023

Template No.: CS\_TP\_BS016 Revision 7 Reference: CS\_WI\_BS005

Page 21 of 48

partial or missing in the listings.

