# **Presentation of Treatment Groups**

For outputs, treatment groups will be represented as follows and in the given order:

Period			Group	Treatment Group	For Tables, Listings and Figures
Run-in Period				Humira	Humira
Randomized Period	Interchangeable	Treatment	Group 1	Humira	Group 1
Randomized Period	Interchangeable	Treatment	Group 2	Hulio/Humira/Hulio	Group 2

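### SAP Section 14 gives continuing medication no stated route into the randomised period, so a summary of that period would show mainly new starts

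*SAP*

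**What the plan says.** SAP Section 14 makes two separate classifications.

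The first divides prior from concomitant use, relative to the first run-in dose. A medication may be concomitant whatever its start date, provided it also meets a second condition: "AND ended on or after the date of first dose of study medication or were ongoing at the end of the study". Continuing use is therefore in scope.

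The second places concomitant medications in a study period, by four rules:

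- Start and end both in run-in: "If Concomitant medication started and ended during Run-in period, it will be part of Run-in period".
- Start in run-in, no end date: "If concomitant medication started during Run-in period and end date is missing it will be part of Run-in period".
- Start after randomisation: "If concomitant medication started during Randomized Interchangeable Treatment Period, it will be part of Randomized Interchangeable Treatment Period".
- Neither date known: "If start and stop date of concomitant medication is missing, then it will be part of Run-in period".

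On the display, the section says "Prior and Concomitant medications will be presented for the Run-in Period Population", grouped by third-level ATC code and preferred name. It does not describe columns. Three other places bear on the point:

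- SAP Section 7.1 fixes the later period: "Randomized Interchangeable Treatment Period is defined as study period from the randomization at Week 12 until Week 28", or last participation for patients who leave early.
- Appendix 1 labels the run-in with one Humira column and the randomised period with Group 1 and Group 2.
- Appendix 3 handles incomplete dates by sorting records into prior, concomitant or post treatment. It does not assign a period.

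**The concern.** Each rule names one period, and the one rule that leads to the randomised period depends on when the medication started, not on when it was taken. A therapy begun before Week 12 and continued through Week 28 is used for the whole randomised period, but no rule puts it there.

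The randomised period is when the switching and non-switching groups differ, and PASI, sPGA and PK are read at its end. A reader who consults a medication summary for that period will want to know what patients were taking alongside study drug. A summary of new starts answers a different question and could be mistaken for a complete account of use.

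The patterns are to be expected here. Under the protocol's exclusion criteria, treatment for latent TB must have begun before study treatment and must continue. Low-potency topical corticosteroids at certain sites are permitted during participation. The first is a start before Week 1 that may run on. The second may begin in run-in and continue.

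**Working it through.** The plan gives no figure to reproduce. The check applies the four rules to ten combinations of start and stop date and compares the result with the periods in which the drug was, or may have been, taken.

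**Inputs.** The rules are those of SAP Section 14, and the period limits come from SAP Section 7.1. Nominal days are assumed: Week n begins on day 7 × (n − 1) + 1. Week 1 is then day 1, Week 12 is 7 × 11 + 1 = day 78, and Week 28 is 7 × 27 + 1 = day 190. In the last column, a missing start is taken as day 1 and a missing end as use to day 190.

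| Start | End | Section 14 gives | Overlap with use |
|---|---|---|---|
| Run-in | Run-in | Run-in | Run-in |
| Run-in | Missing or ongoing | Run-in | Both |
| Run-in | Randomised | No rule | Both |
| Before day 1 | Run-in | No rule | Run-in |
| Before day 1 | Randomised | No rule | Both |
| Before day 1 | Ongoing | No rule | Both |
| Randomised | Randomised | Randomised | Randomised |
| Randomised | Ongoing | Randomised | Randomised |
| Missing | Missing | Run-in | Possibly both |
| Missing | Randomised | No rule | Both |

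**Result.** Of the ten patterns, 3 are placed where the use lies, 2 go to run-in although use extends or may extend past Week 12, and 5 have no rule (3 + 2 + 5 = 10). Eight patterns overlap or may overlap the randomised period. Of these, 2 are placed there, 2 are sent to run-in, and 4 are unplaced (2 + 2 + 4 = 8). The two that are placed there are the two that started there. These are counts of date patterns, not estimates of how many records follow each one.

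**One record followed through.** A drug starts at Week 8 (day 7 × 7 + 1 = 50) and is still taken at Week 28.

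- Run-in overlap: 78 − 50 = 28 days, or 4 weeks.
- Randomised-period overlap: 190 − 78 = 112 days, or 16 weeks.
- Share of use after randomisation: 16 / (4 + 16) = 80%.

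With no end date recorded, Section 14 assigns it to run-in.

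**Does the meaning of a missing end date matter?** The rule is triggered by a missing end date, and Section 14 mentions ongoing use separately. If a medication flagged as ongoing counts as having no end date, it goes to run-in. If it does not, it has no rule. On neither reading does the stated text place it in the randomised period.

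**The case against.** The strongest reply is that allocation by start date is a deliberate and usable convention. SAP Section 19.1 has a matching rule for adverse events: one that began in run-in and has no end date stays in run-in. The modification history shows that the medication logic was revised for version 2.0. A display of therapy newly begun after randomisation is legitimate in itself. But the parallel does not carry over. Adverse events are counted by onset, whereas Section 14 defines concomitant medication so as to include continuing use. Nor is the display labelled as one of new starts.

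Five further points stand and limit the concern:

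- **The table.** A reader might infer a by-arm table for the randomised period. Section 14 describes none. It can only be inferred from the period rules and the Appendix 1 columns, and SAP Section 9 leaves layout to templates that are not in these documents. Sections 11 and 12 show other Run-in Period Population summaries by planned group, so run-in medication might also be shown by arm.
- **The extent.** A reader might also infer that all long-term therapy begun before Week 12 is left out. The text does not go that far. Therapy begun before Week 1, or stopped after Week 12, is unassigned, and a programmer might place it sensibly. Only the missing-end and both-missing cases are expressly sent to run-in.
- **Exclusivity.** The rules do not use the word "only". That a medication belongs to one period is a reading of four rules that each name one.
- **The definition.** There is no outright contradiction with the definition of concomitant, which separates records by first dose and does not allocate periods.
- **The consequence.** Medication that could disturb results is handled elsewhere: PP and PK exclusions (Sections 6.5 and 6.6), deviation review (Section 10.2) and non-responder imputation (Section 17.2.2).

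**Conclusion.** The point holds as an incomplete and partly misdirected allocation rule. Followed as written, Section 14 understates medication use in the randomised period, because two kinds of record that may represent continuing use go to run-in and several others go nowhere. The documents give no medication data, so the number of records affected cannot be stated.

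The conclusion rests on two assumptions: that ongoing medications are normally recorded without an end date, and that some summary by period will be produced. The existence of period rules implies the second.

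The matter is minor. A reader might infer that an incomplete medication summary could bias the equivalence result or the choice of patients analysed. The documents do not support that. The primary ANCOVA in SAP Section 20.2.7 contains treatment, the PASI ratio, weight and the run-in PK value, with no medication term. Exclusions are decided through deviation review, which by Section 10.2 draws on trial-management logs. What is at stake is the accuracy of descriptive summaries.

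**What to change.** Replace the four period rules in SAP Section 14 with one principle: a concomitant medication belongs to every period its use overlaps.

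- **Run-in:** it started before the first randomised dose (for patients without one, on or before last participation), and it ended on or after Day 1 or its end is missing or ongoing.
- **Randomised period:** for patients dosed in that period only; it started on or before the end of the period (Week 28 or last participation), and it ended on or after the Week 12 dose or its end is missing or ongoing.
- **Both dates missing:** count it in run-in and, for patients dosed after randomisation, in the randomised period too.
- **Start missing, end known:** treat the start as no later than Day 1, then apply the rules above.

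The restriction to dosed patients matters because the Run-in Period Population includes run-in failures. SAP Section 4 plans for 370 enrolled and 330 randomised, so about 370 − 330 = 40 patients could otherwise contribute ongoing drugs to a period they never reached. The upper limit keeps out medications begun in follow-up.

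The cost is a short wording change and a small programming change, with no new data. Some medications will appear under both periods, so counts will not add across periods and a footnote should say so. Records whose stop date is merely unknown will be treated as continuing, which may overstate use somewhat. That is in keeping with the worst-case approach Section 14 already takes when a record cannot be classed as prior or concomitant.

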#### 15. STUDY MEDICATION EXPOSURE

Exposure to randomized study medication in weeks will be presented for the Run-in Period Population and SAF separately.

\\ieedc-vnasc01\Biosdata\Viatris\HULIO\HAB34991\Biostatistics\Documentation\SAP Document:

2.0 Author: Version Number:

> Version Date: 29Nov2023

Template No.: CS\_TP\_BS016 Revision 7 Reference: CS\_WI\_BS005

Page 27 of 48

Duration of Run-in period is 11 weeks i.e., Week 1 to Week 10 and duration for Randomized Interchangeable Treatment Period is 16 weeks i.e., Week 12 to Week 26.

The date of first study medication administration will be taken from the eCRF "Exposure (log)" form. The date of last study medication will be taken from the eCRF "End of Study Treatment" form (Date of treatment completion/discontinuation).

Interruptions, compliance, and dose changes are not considered for duration of exposure.

The duration of exposure to IP in weeks and number of IP administrations will be summarized descriptively including n, mean, median, standard deviation, minimum, and maximum for Humira for Run-in Period Population and for each treatment group for SAF. Count and percentage of patient exposed to IP will be provided (Week 1, Week 2, Week 4, Week 6, Week 8, Week 10 for Run-in period, and Week 12, Week 14, Week 16, Week 18, Week 20, Week 22, Week 24, Week 26 for Randomized Interchangeable Treatment Period).

Location of drug administration, number of patients who administered full dose, dose adjusted, and reason of dose adjustment will be tabulated on SAF population.

#### 15.1. Derivations

Duration of exposure in Run-in period (weeks)

= (date of last study medication administration in Run-in period – date of first study medication administration in Run-in period + 1)/7.

If the last IP administration date was unknown,

Exposure duration = (last available visit date in Run-in period – first IP administration date in Run-in period + 1)/7

Duration of exposure in Randomized Interchangeable Treatment Period (weeks)

= (date of last study medication administration in Randomized Interchangeable Treatment Period – date of first study medication administration in Randomized Interchangeable Treatment Period + 1)/7.

If the last IP administration date was unknown,

Exposure duration = (last available visit date in Randomized Interchangeable Treatment Period – first IP administration date in Randomized Interchangeable Treatment Period + 1)/7

### 16. STUDY MEDICATION COMPLIANCE

Compliance to randomized study medication will be presented for the SAF only for the patient who entered Run-in

Document: \\ieedc-vnasc01\Biosdata\\Viatris\HULIO\HAB34991\Biostatistics\Documentation\SAP

Author: Version Number: 2.0

Version Date: 29Nov2023

Template No.: CS\_TP\_BS016 Revision 7 Reference: CS\_WI\_BS005

Effective Date: 01Nov2021

Page 28 of 48

period and Randomized Interchangeable Treatment Period. Compliance will be checked. Treatment compliance for patients will be summarized for 26 weeks along with the number and percent of patients with compliance in each of the following groups:

- Compliant: percentage of compliance =>80% <=110%
- Non-Compliant: percentage of compliance <80% ->110%

Total number of planned injections from week 12 to week 26 is 8.

#### 16.1. Derivations

Compliance with randomized study medication is based on the eCRF "Exposure (log)" form. An administered injection is considered when the question "Was full dose administered?" is answered "Yes".

Compliance is defined as actual number of injections divided by number of assigned injections.

Overall compliance (%) for Run-in period = (Total Number of injections administered in Run-period) \*100/ (Total Planned number of injections in Run-in period)

Overall compliance (%) for Randomized Interchangeable Treatment Period = (Total Number of injections administered in Randomized Interchangeable Treatment Period) \*100/ (Total Planned number of injections in Randomized Interchangeable Treatment Period)

### 17. EFFICACY OUTCOMES

## 17.1. Primary Efficacy

Not applicable.

# 17.2. Secondary Efficacy

The secondary efficacy analyses will be performed for the PP population.

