Sensitivity Analyses: The AUC τ , $_{26\text{-}28}$ and C_{max} , $_{26\text{-}28}$ will be analysed using analysis of covariance (ANCOVA) model on the log transformed scale. This model will include treatment and covariates. Log transformed AUC $_{\tau,\ 10\text{-}12}$ or $C_{max,\ 10\text{-}12}$ will be used as covariates.

The secondary PK endpoint $C_{min\ 26-28}$ will be analyzed in the same way as the primary endpoints. However, even the mean ratio and CIs will be calculated and presented. No formal conclusion is required to be within BE limits.

The secondary PK endpoint $T_{max\ 26-28}$ will be analyzed in a descriptive manner only.

All PK analysis will be performed on the PK population.

Efficacy Analysis:

All secondary efficacy endpoint analyses will be based on the PP population.

The difference in proportions will be calculated as the difference between the observed proportions in each treatment group. An asymptotic 2-sided 90% confidence interval for the difference of proportions will be obtained using the Wald method.

Safety Analyses:

Treatment-emergent AEs, serious AEs and Adverse event of special interest (AESI) will be descriptively summarized by system organ class, preferred term, and treatment group.

Overall, descriptive summaries will be produced as well as according to severity and relationship to the study treatment.

Local tolerance and antibodies to adalimumab will be descriptively summarized by treatment group.

The safety analyses will be performed on the Safety and Run-in Period populations.

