## 6.5.Per Protocol Population [PPP]

The Per Protocol Population (PPP) will contain all randomized patients in the Safety population who have assessments prior to randomization and at least once post-randomization for at least one secondary efficacy endpoint and who do not have any important protocol violations impacting efficacy.

Reasons for exclusion can be, but not limited to:

Non-compliance with the inclusion or exclusion criteria.

Insufficient essential efficacy data for the secondary analysis.

Intake of prohibited medication.

Non-compliance with randomization criteria.

Non-compliance with the study treatment.

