#### • Step 2: Non-responder imputation

Patients will be considered as non-responder if

- discontinued the study treatment before Week 28
- lost to follow up before Week 28 (As per End of study CRF page)
- any severe violation related to any therapy that may significantly impact efficacy assessment before
   Week 28 (which will be decided during

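### PASI and sPGA response is compared only in a per-protocol set whose exclusions overlap the non-responder rule, so an arm imbalance in those exclusions would not reach the responder differences

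*SAP*

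**What the plan says.** **Analysis set.** SAP 17.2 reads: "The secondary efficacy analyses will be performed for the PP population". The protocol synopsis (Statistical Methods, Efficacy Analysis) agrees: "All secondary efficacy endpoint analyses will be based on the PP population". SAP section 6 defines screened, enrolled, run-in, safety, per-protocol and PK populations. It defines no full-analysis set, and the Safety population has no efficacy use.

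**Who leaves the per-protocol set.** SAP 6.5 keeps randomised, treated patients assessed before randomisation and "at least once post-randomization for at least one secondary efficacy endpoint", and "who do not have any important protocol violations impacting efficacy". Its open list of possible exclusion reasons includes "Intake of prohibited medication", "Non-compliance with the study treatment" and "Insufficient essential efficacy data for the secondary analysis", as well as failures of eligibility or randomisation criteria.

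**Who is counted as a failure.** Step 2 of SAP 17.2.2, applied after multiple imputation, makes a patient a non-responder for stopping study treatment before Week 28, for loss to follow-up before Week 28, or for "any severe violation related to any therapy that may significantly impact efficacy assessment before" Week 28.

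**Related rules.** SAP 10.2 finalises the per-protocol set from critical and major deviations that affect the primary analysis, which is PK. SAP 7.4 remaps an early-termination PASI or sPGA score to a scheduled visit within 3 days of the target day; a score that cannot be remapped is not used for efficacy.

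**The concern.** A severe therapy violation that may affect the efficacy assessment is hard to tell apart from an important violation impacting efficacy. Step 2 treats the first as a failure and SAP 6.5 treats the second as a reason to leave the analysis. The SAP does not say which rule applies to a patient who meets both descriptions.

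The choice matters because these events occur after randomisation and may depend on the arm. If switching led to more non-compliance, more prohibited psoriasis therapy or more early dropout, removing those patients would raise the switching arm's responder rate, and the planned efficacy comparison would not reflect the cause. Comparing efficacy in the two arms is a stated secondary objective. SAP 8.3 marks intercurrent events as not applicable, so nothing else in the plan settles how these patients should count.

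**Working it through.** **1. The two rules side by side**

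| Patient after randomisation | SAP 6.5 | Step 2 of SAP 17.2.2 |
|---|---|---|
| Important or severe violation affecting efficacy | Excluded | Non-responder, if still in the set |
| Prohibited medication | Can be excluded | Non-responder if judged a severe therapy violation |
| Non-compliance with treatment | Can be excluded | Not named, unless treatment was stopped or the violation is severe |
| Stopped or lost, with a usable post-randomisation score | Can stay | Non-responder |
| Stopped or lost, no post-randomisation score | Outside the set | Never reached |
| Eligibility or randomisation failure | Can be excluded | Not a Step 2 category |

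The first two rows are the overlap. The fifth is a gap: SAP 17.2.2 names Weeks 12, 16, 20 and 28 for the imputation, so a patient who stops soon after the first switch, without a score that maps to Week 16, may have nothing usable. SAP 6.5 does not say whether an unmapped score satisfies its minimum-data condition.

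**2. Inputs for the illustration**

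The plan gives no sample size, margin or expected response for efficacy, so it has no efficacy figure to reproduce. Its PK figure does reproduce: the smallest N with per-endpoint power of at least 0.9487 is 282, as SAP section 4 states. It has no bearing on this point.

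- From SAP section 4: 330 randomised, 330 / 2 = 165 per arm.
- Assumed, not in the documents: 85% response in retained patients of both arms; 5 Humira versus 12 switching patients excluded, or 3 versus 15; every excluded patient a non-responder in the full set.

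**3. Differences (switching minus Humira)**

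The per-protocol difference is 0.85 - 0.85 = 0 in both cases.

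Full-set rate = 0.85 x (165 - excluded) / 165.

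- 5 versus 12: 0.85 x 153/165 - 0.85 x 160/165 = 0.788 - 0.824 = **-3.6 points**
- 3 versus 15: 0.85 x 150/165 - 0.85 x 162/165 = 0.773 - 0.835 = **-6.2 points**

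**4. Precision**

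90% Wald interval = difference ± 1.645 x sqrt[p1(1 - p1)/165 + p2(1 - p2)/165].

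- 5 versus 12: standard error 0.0435, interval -10.8 to +3.5 points
- 3 versus 15: standard error 0.0436, interval -13.4 to +1.0 points

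**5. Dependence on the assumptions**

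If only a fraction f of the excluded patients count as non-responders and the rest respond at 85%, the difference is -0.85 x f x (difference in exclusions) / 165. At f = 0.5 this gives -0.85 x 0.5 x 7/165 = -1.8 points and -0.85 x 0.5 x 12/165 = -3.1 points.

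If 5% versus 15% are excluded and all count as failures, the difference is -0.10 x response rate: -6.0 points at 60% response, -7.5 at 75% and -9.0 at 90%. The per-protocol difference is 0 throughout.

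**The case against.** Several counter-arguments are sound.

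- **The overlap is not complete.** A reader might infer that the Step 2 violation rule has nobody left to act on. The documents do not support that. The listed reasons in SAP 6.5 are possible grounds for exclusion, not automatic ones. SAP 10.2 ties the set to deviations affecting the primary PK analysis, so a prohibited psoriasis therapy that affects PASI but not adalimumab PK could stay in and be counted as a failure. The two sections also use different terms, important and severe, without equating them. The Step 2 sentence on who decides is cut short in the public text, so further detail may exist.
- **Discontinuation and loss still count.** Patients who stop or are lost after a usable post-randomisation assessment can stay in the set and be counted as failures.
- **The imbalance is not hidden from the report.** A reader might infer that it could not be seen at all. SAP 10.1 tabulates discontinuations with reasons by planned treatment group, and the reasons for exclusion from each population. SAP 10.2 covers deviations and section 16 covers compliance in the Safety population. These tables show an imbalance but do not turn it into a response difference with an interval.
- **Set membership is agreed before unblinding** (SAP section 6). This limits selective exclusion. It does not restore the randomised comparison if the exclusions follow from treatment.
- **Efficacy is secondary, with no margin or test, and per-protocol use is prespecified in both documents.** That limits the weight of the point. It supports keeping the per-protocol analysis, not making it the only one.

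**Conclusion.** The point holds as a gap in the supportive efficacy evidence. The only planned PASI and sPGA comparisons sit in a set that can lose, after randomisation, patients whom Step 2 would in part count as failures. An arm imbalance in those losses would not enter the responder differences or their intervals.

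The shifts of -3.6 and -6.2 points are illustrations, not predictions. They rest on assumed exclusion counts, an assumed 85% response and every excluded patient counted as a non-responder, and they shrink if some enter with their observed response. Both full-set intervals include zero.

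The interchangeability decision rests on the PK endpoints in the PK population and is unaffected.

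**What to change.** 1. Keep the per-protocol analysis. Add the same Week 28 multiple-imputation plus non-responder analysis in all randomised, treated patients (the Safety population), by randomised arm, and report it beside the per-protocol result.
2. In that run, state how patients with no usable post-randomisation score are handled, so that those who stop treatment or are lost early are counted under Step 2.
3. Reconcile SAP 6.5, SAP 10.2 and Step 2 of SAP 17.2.2 so that, in the per-protocol run, each type of violation is either an exclusion or a non-response. State whether the per-protocol set is driven by deviations affecting efficacy or by those affecting PK.
4. Do not delete the Step 2 violation rule before item 3 is done. If such patients remain in the set, deletion would let them count as responders on their observed scores.

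The cost is one more set of efficacy tables from existing code, with somewhat lower responder rates in that set. No new data are needed, and the sample size, which rests on PK, does not change.
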